6.2 Timing of disease activity and weight assessment

Study procedures are graphically summarized in the attachment "Study chart".

Patient-reported outcomes described in 5.1 and 5.2 will be obtained at T-4, T0, T1, T2, T3, T4, T5, T6, T7, T8, T12, T16, and T20. Patients will be instructed to fill the questionnaires at appropriate intervals and bring them at the subsequent office visits.

During the office visits (T0, T8, T12, T16, T20), a rheumatologist will perform medical interview with special focus on adverse events and routine musculoskeletal visit; weight and height will be measured and recorded.

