7. SAFETY MONITORING

7.1 Blood tests

Following the abovementioned clinical guidelines^{8, 9}, safety will be monitored through regular blood and urine tests:

- Before VLCKD and every 4 weeks (T0-T4-T8): complete blood count (CBC), creatinine, blood urea nitrogen (BUN), uric acid, glucose, HbA1c, insulin, total cholesterol, HDL-cholesterol, LDL-cholesterol, triglycerides (serum), ALT, AST, γ -GT, total and direct bilirubin, Sodium, potassium, calcium, magnesium, inorganic phosphate, complete urinalysis and microalbuminuria, 25-hydroxyvitamin D, C-reactive protein
- Before VLCKD and at the end of VLCKD (T0-T8): Body composition by whole body DEXA

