7.2 Adverse events monitoring

Adverse events will be systematically monitored during each office visits (see 6.1); any potential adverse event will be reported on CRF. In case of adverse event, the investigator, in agreement with the patient, will decide if continue or withdraw from the study. Furthermore, the patient and his/her general practitioner will be able to communicate to the study staff any suspect adverse events using the phone number reported in patient information sheet.

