9. STATISTICAL ANALYSIS

Given the exploratory nature of the study, an arbitrary number of 20 fibromyalgia and 20 symptomatic knee osteoarthritis patients will be recruited from Rheumatology Outpatient Clinic – IRCCS Istituto Ortopedico Rizzoli, Bologna, Italy. Patients' associations will be involved for volunteer engagement.

Primary measures of efficacy (change in FIQ total score and WOMAC total score, for fibromyalgia and osteoarthritis, respectively) will be compared using paired-sample Student's T tests at time T-4, T0, T8, T20. Analysis of covariance (ANCOVA) will be used to evaluate the effect of baseline disease severity and BMI on change in primary efficacy measures.

Furthermore, other exploratory analyses will be performed:

- Change in secondary outcome measures at T-4, T0, T8, T20;
- Correlation between change in body weight ($\Delta\text{weight}_{T0-T8}$) and change in primary (ΔFIQ_{T0-T8} or $\Delta\text{WOMAC}_{T0-T8}$) and secondary outcome measures;
- Time course of %change in FIQ total score and WOMAC total score from T-4 to T20;
- Student's T test for difference in ΔFIQ_{T0-T8} or $\Delta\text{WOMAC}_{T0-T8}$ in patients who achieved and maintained ketosis during the ketogenic phase (urinary ketones > +5 from week 1 to week 8) vs patient who did not maintained ketosis.

Both per-protocol (PP) and intention-to-treat (ITT) analyses will be performed.

All analyses will be performed using the Statistical Software for Social Sciences (SPSS, IBM) version 23.

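### The protocol promises an ITT analysis of FIQ and WOMAC change but plans no T8 or T20 score for a patient who withdraws after an adverse event

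*Protocol*

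**What the plan says.** Section 9 of the protocol names change in FIQ total score (fibromyalgia) and in WOMAC total score (knee osteoarthritis) as the primary efficacy measures. They are compared by paired-sample "T tests at time T-4, T0, T8, T20". On analysis sets it says: "Both per-protocol (PP) and intention-to-treat (ITT) analyses will be performed". It calls the study exploratory and the 20 patients per disease an arbitrary number. It gives no expected dropout rate.

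Section 7.2 covers what happens after an adverse event: "In case of adverse event, the investigator, in agreement with the patient, will decide if continue or withdraw from the study".

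Section 6.2 sets one questionnaire schedule, which includes T-4, T0, T8 and T20, and describes the route by which forms reach the study: "Patients will be instructed to fill the questionnaires at appropriate intervals and bring them at the subsequent office visits". It makes no separate provision for patients who have withdrawn. No other section shown does so, and none describes a final score at the time of withdrawal.

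**The concern.** There is no randomised comparison here, so ITT can only mean all patients enrolled, or all who start the diet. Its value beside the per-protocol result is that it keeps patients for whom the diet did not work out. Patients who leave after an adverse event are among those most relevant to that purpose.

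A paired test at T8 or T20 needs a score at that time. If leaving the diet because of an adverse event also means leaving the study, and no score is planned afterwards, the ITT analysis lacks the data that would separate it from an analysis of those who stayed. An analysis plan can say how to impute a missing T8 score, but it cannot supply one that was never collected. That is why the point belongs in the protocol, even though ITT definitions and missing-data rules may properly sit in an SAP that is not shown.

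**Working it through.** The plan states no figure on this point, so there is none to reproduce. The check has two parts.

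**1. Which comparisons a withdrawn patient can enter**

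Inputs: the four time points in Section 9, and no planned score after withdrawal (Sections 6.2 and 7.2).

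- Possible pairs among T-4, T0, T8 and T20: 4 × 3 / 2 = 6.
- A patient who leaves after T0 but before T8 has only T-4 and T0 observed, and so enters 1 of the 6 pairs (T-4 vs T0). That pair precedes the diet. The other 5 need T8 or T20.
- A patient who leaves after T8 but before T20 has three of the four scores, and so enters 3 × 2 / 2 = 3 of the 6 pairs. Only the T20 comparisons are lost.

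**2. How far the observed mean change could depart from the all-patient mean**

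All three inputs are assumptions, because the protocol gives no rate of dropout or of withdrawal after an adverse event:

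- d = fraction leaving before T8. Values 0.1, 0.2 and 0.3 are 2, 4 and 6 of 20, leaving 18, 16 and 14 pairs.
- r = mean change in leavers divided by mean change in those who stay.
- q = fraction of leavers who still give a T8 score, taken to have the same mean change as the other leavers.

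With the mean change of those who stay set to 1:

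- Mean among patients with a score = [(1 − d) + d·q·r] / [(1 − d) + d·q]
- Mean among all patients = (1 − d) + d·r
- Relative error = (first / second) − 1

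With no scores from leavers (q = 0), the first mean is 1 and the error is 1 / [(1 − d) + d·r] − 1. Example: d = 0.2, r = 0 gives 1 / 0.8 − 1 = 25%. With half of the leavers scored (q = 0.5), the same case gives (0.8 / 0.9) / 0.8 − 1 = 11.1%.

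| Scores from leavers | r | d = 0.1 | d = 0.2 | d = 0.3 |
|---|---|---|---|---|
| None (q = 0) | 0 | +11.1% | +25.0% | +42.9% |
| | 0.5 | +5.3% | +11.1% | +17.6% |
| | 1 | 0% | 0% | 0% |
| | 1.5 | −4.8% | −9.1% | −13.0% |
| Half (q = 0.5) | 0 | +5.3% | +11.1% | +17.6% |
| | 0.5 | +2.5% | +4.9% | +7.3% |
| | 1 | 0% | 0% | 0% |
| | 1.5 | −2.3% | −4.0% | −5.4% |
| All (q = 1) | any | 0% | 0% | 0% |

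The q = 0 rows describe an analysis of observed scores without imputation. With imputation, the error depends on the rule chosen and on how far earlier scores predict the missing ones.

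**The case against.** The strongest reply is that the protocol is silent here rather than wrong. Nothing in it forbids scoring a patient after the diet stops, and Section 6.2 lists the scores up to T20 without excepting patients who are off the diet. The sentence in Section 7.2 concerns study participation and does not mention the diet, so continuing could include staying in the study off diet. Section 7.3, on pregnancy, names stopping the diet and withdrawal from the study as separate steps, although there one leads to the other. Promising ITT while allowing withdrawals is not in itself a contradiction.

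Most of this stands and limits the claim. A reader might infer that the ITT analysis must collapse into a completers' analysis. The documents do not support that. It holds only if missing values are not imputed, and weekly scores are planned between T0 and T8 from which an early leaver's value might be imputed. The ITT set also keeps other content: Section 9 compares T0 to T8 change between patients who did and did not maintain ketosis, so patients who fail to maintain ketosis are expected to be scored at T8. A reader might also infer that the weekly forms of early leavers would be lost. That depends on the study chart attachment, which is not shown, and those scores do not enter the primary tests.

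What the reply does not remove is the gap in data collection. A favourable reading of Section 7.2 is possible but not stated, and for a patient who does withdraw from the study no section shown plans a T8 or T20 score.

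**Conclusion.** The point holds as a gap between the analysis promised in Section 9 and the follow-up described in Section 7.2. On a literal reading, the ITT result at T8 and T20 rests on patients who stayed, or on imputation from earlier scores, as far as withdrawals after an adverse event are concerned.

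The direction and size of any bias are unknown. The illustrations run from −13% to +43%, with zero error if leavers change as much as those who stay. The upper end needs 6 of 20 patients to leave before T8 with no lasting change. The 10% to 30% rates are assumed for all leavers. Only withdrawals after an adverse event are at issue, so the affected share may be smaller.

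The study is an uncontrolled exploratory pilot, so what is at stake is the interpretation of the within-patient change, not a confirmatory test. The change is worth making because it is cheap and because scores not collected at the time cannot be recovered.

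**What to change.** 1. In Section 7.2, distinguish a patient who stops the diet from one who leaves the study. The clinical rules on when the diet stops stay as they are.
2. Unless the patient withdraws consent, keep collecting the self-administered FIQ or WOMAC at T8 and T20, by post, by e-mail or at a visit.
3. In Section 9, state that these scores enter the ITT analysis.

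The cost is a few sentences in the protocol, a matching line in the patient information, and a few extra questionnaires to send and chase. Some patients who stop the diet will decline, so the gain is partial. In the illustration with no lasting change in leavers, scores from half of them reduce the error from 11%, 25% and 43% to 5%, 11% and 18%.

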10. STUDY COSTS

No additional costs are attributable to this study except the provision for protein preparations required during the ketogenic phase of the diet. For this cost, we asked producers of VLCKD supplements a free supply of preparations to cover the requirements. Logistica Food srl, located in Manoppello (PE), [name] preliminary agreed (see attachment) to cover the requirements of the study. To preserve sensitive information of recruited patients, the orders covering product requirement for the entire study period will be anonymously placed by the Dietetic Service, IRCCS Istituto Ortopedico Rizzoli; subsequently the products will be hand-delivered by a dietician investigator to individual patients.

11. PUBLICATION OF RESULTS

The results from this study will be published or shown at scientific conferences. The final publication of the study results will be written by the Principal Investigator.

12. SPONSOR ROLE AND RESPONSIBILITY

The promoter is the sole owner of the data and is responsible of all the clinical trial activities from study design, development, data collection, management, analysis, interpretation of data, writing and the decision to submit the report for publication written by the Principal Investigator.

